2.5 Intervention

Table 2 presents the details of the visits and the sample collection processes.

Table 2. Visits details and sample collection process in chronological order.

Visits/Sampling days	Description
Visit 1	
The researcher visits the participant one day before the sampling day 1 (6 days after being in the urban/rural setting) and the following procedures are performed:
 
 • Administrates the consent form and receives it signed by the participant • Administrates the Questionnaire A and Chronotype Questionnaire and receives them completed by the participant • Provides coded vials for urine sampling in plastic bag and explains • Provides activity diary and explanations • Places temperature sensors on the participant (after activating them on place) and explains • Provides the instructions for urine collection and temperature sensors

	
 • Arranges appointment for the sample collection two days later (ideally in the morning)
Sampling day 1	
The participant is wearing the sensors continuously from the previous day and collects the urine voids of the day (at least 4) except for the first morning void. The participant stores the urine vials in a plastic bag in the freezer/fridge. The participant notes in the activity diary, the activities of the day (including entrance/exit from buildings, sleep/wake cycle, physical activities and meals) and their corresponding time and the times that each urine void was collected.

Visit 2	
The participant collects the first morning void of the day after the sampling day and continues wearing the temperature sensors and noting in the diary.
 
The researcher visits the participant one day after the sampling day on the arranged time and the following procedures are performed:
 
 • Collection of the urine samples and sensors • Collection and check of the completed activity diary • Sensors data are transferred immediately on a laptop, to check that data were recorded • Arrangement for the next visit that will take place in the other setting (urban/rural) with at least 2 days of washout period and on the 6th day in the alternate setting.

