3.2 Populations

Depending on the analysis, different characteristics for inclusion are defined in the population. For example:

In the Full Analysis, population is defined as:

- All subjects who were randomised.
- All subjects who completed both sampling days providing complete follow-up, independent of the duration of the sampling days.
- All subjects who completed both sampling days providing complete follow-up, independent of the stability of sleep/wake cycles and meal intakes.
- All subjects who completed both sampling days providing complete follow-up, independent of the number of received urine vials.

In the Final Analysis, population is defined as:

- All subjects who completed both sampling days providing complete follow-up, except those who dropped out.
- All subjects who adhere to the major criteria in the protocol (e.g. all subjects who stayed healthy or did not travel to another country within the study or completed both sampling days and completed the whole study duration).
- All subjects who did not substantially deviate with regards to sleep/wake cycles and meal intakes
- All subjects except those that have a health problem (diabetes and hypertension) and did not know by the beginning of the study.
- All subjects except those women that were pregnant and did not know by the beginning of the study.

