3.4 Unadjusted and adjusted analyses

The urinary variables will be used with adjustment for creatinine levels to account for urine dilution. If outcomes are not normally-distributed and the analyses require the normality assumption, then outcomes will be log-transformed (natural logarithm).

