3.9 Primary analysis of outcomes

3.9.1 Cosinor method

An exploratory analysis will be formed by plotting the data as a function of time for each sampling day. This will allow for visual observation of possible trends and for comparisons between sampling days. Residuals will also be plotted as a function of time that will provide valuable information on how to proceed for further analysis. A histogram will also be used to assess normality of the results.

Since prior information suggests a presence of rhythm with period of 24-hours, data will be stacked in classes in an attempt to reduce noise and reveal the rhythm's waveform. Class means will be used to test for a statistically significant time effect.

Once a rhythm has been validated, the single cosinor method will be used to model the rhythm by fitting a cosine curve, a procedure similar to the least square methods (Cornelissen, 2014). For each subject, a single-component cosinor will be created for each sampling day, and for each group, a population-mean cosinor will be created for each sampling day. These methods also involve certain assumptions that need to be satisfied hence; regression diagnostics will be implemented at this stage to assess the model's adequacy. Further statistical testing will be implemented to test the equality of parameters such as the MESORs, amplitudes and acrophases (Cornelissen, 2014) of the two groups in the two settings.

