3.9.3 Primary Analysis

TEMP Study

Linear mixed effect models of the adipokines, cortisol and melatonin levels will be used as a function of the treatment (rural vs urban), accounting for both between and within subject variability by having random intercepts for the participants with unstructured covariance matrix. Non-linear mixed effects models of the adipokines, cortisol and melatonin levels, accounting for their diurnal variation as a function of the treatment, will be also constructed.

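### The linear mixed model of hormone level in 3.9.3 has no time-of-day term, so its setting effect would absorb any difference in void timing, and no time-adjusted analysis is named as decisive.

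*SAP*

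**What the plan says.** **The linear model.** Section 3.9.3 gives the first primary model as follows: "Linear mixed effect models of the adipokines, cortisol and melatonin levels will be used as a function of the treatment (rural vs urban". Its random part is described as "accounting for both between and within subject variability by having random intercepts for the participants with unstructured covariance matrix". No clock-time term is named.

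**The other analyses.** The same section adds non-linear mixed models "accounting for their diurnal variation as a function of the treatment, will be also constructed". Section 3.9.1, also under the primary-analysis heading 3.9, says that "prior information suggests a presence of rhythm with period of 24-hours". It fits a cosinor per subject and sampling day and then tests MESORs, amplitudes and acrophases.

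**The sampling.** In Table 2 of section 2.5 the participant "collects the urine voids of the day (at least 4) except for the first morning void", and collects the first morning void of the following day. There is a minimum but no maximum, and no fixed clock times. The diary holds "their corresponding time and the times that each urine void was collected".

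**Adjustment, analysis sets and multiplicity.** Section 3.4 says: "The urinary variables will be used with adjustment for creatinine levels to account for urine dilution". In section 3.2 the Full Analysis keeps subjects "independent of the number of received urine vials". Section 3.5 applies the Benjamini-Hochberg method to every regression parameter of the primary and post-hoc analyses.

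**The concern.** The plan expects the outcomes to vary with the clock, lets participants set the sampling times, and then compares settings in a linear model that ignores the clock. Void pattern could plausibly follow setting, through heat, fluid loss and routine. If it does, the setting coefficient carries part of the rhythm.

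The stated safeguards do not reach this:

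- Creatinine adjustment deals with dilution, not timing.
- A participant intercept removes stable differences between people, not a within-person change between settings.
- Randomising the order does not help if the void pattern moves with the setting itself.

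At stake is a discovery that reflects when urine was passed rather than how much hormone was secreted. There is also a loss of power that needs no timing difference at all.

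**Working it through.** **The plan's own figure.** The sample size in 2.9 uses one pair of leptin values per subject. With a within-subject SD of 3.53 and a difference of 1.9, n = 2 × (3.53 × (1.960 + 0.842) / 1.9)² = 54.2, so 55. With the t distribution, 57 is the smallest n that reaches 80% power (80.6%; 56 gives 79.9%). The stated 57 is reproduced. It has no time input, so this point does not change it. I use 57 subjects below.

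**Assumptions.** The SAP gives no void counts by setting, void times, rhythm amplitude or peak time. All of these are assumed here, and there is no true setting effect in any scenario.

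**Check 1: two-level profile.** Take n day voids at level 1 and one overnight void at level r, averaged plainly.

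- Raw mean = (n + r)/(n + 1).
- Log-scale ratio = exp[ln r × (1/(n₁+1) − 1/(n₂+1))].
- For r = 5 and 4 against 6 day voids: raw (9/5)/(11/7) = 1.145; log exp[1.609 × (1/5 − 1/7)] = 1.096.

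| Day voids | r | Raw ratio | Log-scale ratio |
|---|---|---|---|
| 4 v 6 | 2 | 1.05 | 1.04 |
| 4 v 6 | 3 | 1.09 | 1.07 |
| 4 v 6 | 5 | 1.15 | 1.10 |
| 4 v 6 | 10 | 1.23 | 1.14 |
| 4 v 8 | 5 | 1.25 | 1.15 |

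**Check 2: cosine rhythm of amplitude A.** Urban voids are at 10, 14, 18, 22 and 07 h. The spurious rural-minus-urban difference is the difference in mean cos(2π(t − peak)/24), times A. The range is over peaks at 0, 3, 8, 12 and 18 h.

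| Rural pattern | Difference, in units of A |
|---|---|
| One extra void at 03 h | −0.16 to +0.21 |
| One extra void at midday | −0.13 to +0.13 |
| 22 h void missing | −0.27 to +0.27 |
| All voids 2 h earlier | −0.13 to +0.12 |
| All voids 1 h earlier | −0.06 to +0.06 |
| Seven voids (9, 11, 13, 16, 19, 22, 06 h) | −0.06 to +0.06 |

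For example, with an extra 03 h void and a 03 h peak, the urban mean cosine is −1.173/5 = −0.235, the rural mean is (−1.173 + 1)/6 = −0.029, and the difference is 0.206.

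**Check 3: simulation.** There were 57 subjects and 150 runs per row. A, the residual SD and the between-subject SD were all 1, and individual void times varied with an SD of 0.75 h. Each cell gives the mean setting estimate and the share of runs with p < 0.05. The Monte Carlo standard error at 5% is √(0.05 × 0.95/150) = 1.8 percentage points.

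| Rural pattern | Peak | No time term | With cosine and sine |
|---|---|---|---|
| Same times | 03 h | 0.005; 2.7% | 0.004; 4.7% |
| Same times | 08 h | −0.007; 1.3% | −0.007; 8.0% |
| Extra 03 h void | 03 h | 0.204; 54% | 0.003; 6.7% |
| Extra 03 h void | 08 h | 0.041; 1.3% | 0.002; 2.7% |
| 1 h earlier | 03 h | 0.029; 3.3% | 0.000; 5.3% |
| 1 h earlier | 08 h | 0.062; 4.7% | 0.001; 4.0% |
| 2 h earlier | 03 h | 0.079; 6.7% | 0.007; 6.7% |
| 2 h earlier | 08 h | 0.123; 14% | 0.004; 3.3% |

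**Why matched times still cost power.** At the five reference times and a 03 h peak, the cosine has mean square 1.817/5 = 0.363 and squared mean 0.055, so variance 0.308. The residual variance rises from 1 to about 1.31, and the model's standard error by √1.31 = 1.14. The rhythm itself cancels in the contrast, so a nominal 1.96 acts like 1.96 × 1.14 = 2.24, a true level of about 2.5%. This agrees with the simulated 2.7%.

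**The case against.** The strongest reply is that the plan already adjusts for time of day twice. The MESOR is a rhythm-adjusted mean, and 3.9.1 tests it. The non-linear models in 3.9.3 are built for diurnal variation. This stands. A reader might infer from the linear model that the SAP ignores the clock, or that its only primary contrast is biased, and the document supports neither. What remains is narrower: three analyses bear on level, none is decisive, and the unadjusted one counts towards significance under 3.5. The cosinor is also conditional on a rhythm having been validated first.

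A second reply is that no bias has been shown. This also stands. The SAP gives no void data by setting, and some differing patterns nearly cancel: seven voids spread over the day gave at most 0.06A. A reader might infer that heat means fewer day voids, so that a night-peaking hormone would look raised in the city. Nothing in the SAP establishes that direction. The 54% comes from an unfavourable case in which the extra void falls on the peak.

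Third, the single overnight void in Check 1 is a simplification. Table 2 does not limit night voids to one, and 2.1 speaks of collecting every void on the day. Check 2 does not rest on that simplification.

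Fourth, irregular sleep and meals are grounds for exclusion in 2.3, and the Final Analysis in 3.2 removes substantial deviations. This narrows the routine-related route but sets no rule for void number or timing.

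**Conclusion.** The point holds in a limited form. The linear level model in 3.9.3 omits time of day, and its setting effect is open to confounding by void timing if timing differs between settings. Under the assumed patterns the spurious difference runs from negligible to about 0.27 of the rhythm's amplitude, or a ratio of 1.04 to 1.25 in the two-level illustration. A uniform 1-hour shift is harmless in practice (at most about 0.06A, with rejection no higher than 4.7%). These figures show what could happen; they do not estimate what will happen in this trial.

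The power loss is firmer. It needs only the rhythm that the SAP expects, although its size depends on an amplitude that the SAP does not give. Because the plan has time-adjusted analyses alongside, this is a cheap improvement and a missing statement of priority, not a fatal flaw.

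**What to change.** In 3.9.3, do one of the following for each hormone:

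- Add 24-hour cosine and sine terms of the recorded void time to the linear mixed model and, if wanted, an indicator for the first morning void.
- Name the setting difference in MESOR from the non-linear mixed model as the primary level contrast, with the linear model as supportive.

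In either case, report void number and void times by setting, so that readers can see whether timing differed.

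The cost is a few lines of SAP text and two or three extra parameters per hormone in the linear model. The diary already records the times of collected voids, so no new data are needed. The additive terms assume one rhythm for both settings; where a change in rhythm is the question, the non-linear model is the better place for it.

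A daily mean weighted by hours since the previous void is not a good substitute. It needs the time of the sampling day's own first morning void, which is not collected and may not be recorded.

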2.1 General aspects

A 2 x 2 cross-over pilot study of healthy adults is proposed to prospectively describe the effect of ambient temperature gradient on diurnal hormonal secretion patterns. A total of 50-60 subjects will be followed for a period of 7 days firstly in an urban environment or in a village of the mountainous rural environment of Troodos and later, for the same period, in the alternate setting, during the summer period in Cyprus. The two settings will allow for the comparison of the circadian patterns of hormones secreted by the adipose tissue among different gradient temperature changes. Continuous quantification of skin temperatures on one day in each setting will allow for characterization of how skin temperature is affected by ambient temperature. Collection of all urine voids on one day in each setting will allow for quantification of the hormone secretion by the adipose tissue. In Table 1 the study characteristics of the non-pharmacological intervention are presented and in Figure 1 the order and duration of various procedures of the study are displayed.

Table 1. Study characteristics

Study Design	Randomised cross-over trial
Study groups	
Two study groups:
 
Group A: People initially staying in their permanent house in the urban area and then moving to the rural area for at least 7 days (Troodos Mountains – holiday house).
 
Group B: People initially staying in the rural mountainous area for at least 7 days (Troodos Mountains – holiday house) and then returning to their permanent house in the urban area.

Blinding	
The blinding of the participants to group assignment is not possible with the present study design. The blinding of the researchers to the subjects' identity is achieved by the coding of all study materials (urine containers, temperature sensors, questionnaires and diaries). The study personnel who will obtain the outcome measurements will be not informed of the group assignment. The personnel who will deliver the

intervention will not take any outcome measurements. All outcome assessors and data analysts will be kept masked to the allocation.

Randomisation Random allocation will be made in blocks in order to keep the sizes of treatment groups similar. Block randomisation with block size=30 and subjects no=60, will be performed using the function RAND() in Excel, that provides a random generated list, by an investigator with no clinical involvement in the trial

[figure not shown]

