2.9 Sample Size

To estimate the sample size, the sample size program by the MGH Biostatistics Center was used (Schoenfeld, 2010). We used the paired t test study design for calculating the power of this test, assuming that each subject has a pair of values (one for the urban setting and one for the rural mountainous setting). The variable used for the estimation of the sample size was one of the adipokines (serum leptin), since it is one the primary outcomes for the trial and there is no available information for urinary adipokines.

The input parameters were: significance level, within patient standard deviation, power and minimal detectable difference in means. Based on the literature, the within subject standard deviation of plasma leptin was assumed to be 3.53 ppb for females and 0.01 ppb for males (Saad et al., 1998), and we hypothesized a minimal detectable difference in leptin levels between the urban and rural mountainous settings to be atleast 1.9 ppb, based on other intervention studies (Hibi et al., 2017; Fontes-Villalba et al., 2016). Assuming a power of 80% and a two-sided 5% significance level, the sample size for this two-treatment crossover study was estimated to be 57 subjects.

3 Statistical Analysis

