3.7 Derived and Study Variables

Table 3 includes all variables that will be collected, the type of variable and the file that will be included, whereas in Table 3 there is a description of the frequency and timing of relevant variable observations and assessments.

Table 3. List of all variables collected through the study

File	Description	Variables	Type
Quest A	Baseline Characteristics	BMI	Continuous
		Age	Continuous
		Education	Categorical (4 Levels)
		Work	Continuous
		Working Experience	Continuous
		Smoking	Categorical (3 Levels)
		Cigarettes/day	Continuous
		Years smoking	Continuous
		Age ex-Smoker	Continuous
		Alcohol	Categorical (4 Levels)
		Alcohol Units	Continuous
		Exercise	Categorical (2 Levels)
		Exercise Hours	Continuous
		A/C Rural	Categorical (4 Levels)
		A/C Urban	Categorical (4 Levels)
		Travel	Categorical (2 Levels)

TEMP Study

		Airplane Frequency	Categorical (3 Levels)
		Screen Hours	Continuous
		Health	Categorical
Chronotype Quest	Sleep/Wake Cycles		
Diary	Meal Intakes	Time / Meal Time / Drink Time	Continuous
		Diary / Meal Description / Drink Description	Categorical
Urine Analysis	Outcome	Adipokines (leptin, adiponectin, ghrelin)	Continuous
	Exposures	Cortisol Melatonin Metabolites (metabolomics)	Continuous
Temperature Analysis	Exposures	Skin temperature Ambient air temperature	Categorical/continuous

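### Section 3.9.3 does not define the record unit of the primary linear mixed model; if single voids enter, its stated random-effects structure can give a rural-versus-urban standard error that is too small or too large

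*SAP*

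**What the plan says.** Section 3.9.3 relates hormone levels to rural versus urban setting in linear mixed models, "accounting for both between and within subject variability by having random intercepts for the participants with unstructured covariance matrix". No other random effect is named, and setting is the only fixed effect. The next sentence adds non-linear mixed models that account for diurnal variation, again without stating how records are nested.

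The SAP points two ways on what one record is.

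- **One value per setting.** Section 2.9 sizes the trial "assuming that each subject has a pair of values (one for the urban setting and one for the rural mountainous setting").
- **Single voids.** Section 2.1 plans "Collection of all urine voids on one day in each setting". Under Table 2 in section 2.5 the participant "collects the urine voids of the day (at least 4) except for the first morning void", then adds the first morning void of the following day, so at least 5 voids per setting. The diary records "the times that each urine void was collected". No section reduces these voids to one value, and section 3.2 admits participants to the Full Analysis "independent of the number of received urine vials".

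Section 3.9.1 expects a daily rhythm: "prior information suggests a presence of rhythm with period of 24-hours". It fits a cosinor per participant and sampling day once a rhythm has been shown.

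**The concern.** Setting changes only between sampling days, never within one. If voids are the records, two features of the data bear on the setting contrast.

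1. Voids from one day share whatever was particular to that participant on that day. A participant intercept spans both days and cannot absorb this, so the model treats those voids as more independent than they are. The standard error is then too small.
2. A 24-hour rhythm not in the model goes into the residual, although it largely cancels from the contrast when voids fall at similar clock times in both settings. The standard error is then too large.

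This model covers all five hormones, and its parameters enter the false discovery rate procedure of section 3.5. Two competent analysts could fit different models from the same sentence and report different p-values, and the choice could be made after the data are seen.

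**Working it through.** **1. The plan's own figure.** Inputs from section 2.9: within-subject SD 3.53 (females), difference 1.9, two-sided 5%, power 80%. With one value per setting, the SD of the difference is √2 × 3.53 = 4.99. The paired t test (noncentral t) needs 57 participants, with power 0.806. The normal approximation gives 2 × (3.53 × 2.802 / 1.9)² = 54.2, so 55. The stated 57 is reproduced, and it rests on one value per setting.

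**2. One-value reading.** With one record per participant per setting, a participant random intercept is equivalent to the paired comparison. Its standard error is valid.

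**3. Void reading, closed form.** Let n = 57, m = 5 voids per setting and void residual variance 1. Let d be the day-within-participant variance (day share d/(d + 1)) and r the variance of the rhythm over the void times. The SAP gives neither d nor r; all values below are assumptions. Void times are taken as equal in both settings.

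- True variance of the setting contrast: (2/n)(d + 1/m).
- Residual variance pooled by the participant-intercept model: R = [56(1 + 5d) + 456(1 + 1.25r)] / 512, where 56 = n − 1 and 456 = 2n(m − 1).
- Variance reported by the model: (2/n)(R/m).
- Ratio of reported to true standard error: √[(R/5)/(d + 0.2)]. Rejection when there is no difference: about 2[1 − Φ(1.96 × ratio)].

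| d (day share) | r | R | SE ratio | Rejection |
|---|---|---|---|---|
| 0 (0) | 0 | 1 | 1.00 | 5% |
| 0.25 (0.2) | 0 | (126 + 456)/512 = 1.137 | √(0.227/0.45) = 0.71 | 16% |
| 1 (0.5) | 0 | (336 + 456)/512 = 1.547 | √(0.309/1.2) = 0.51 | 32% |
| 0 (0) | 1 | (56 + 1026)/512 = 2.113 | √(0.423/0.2) = 1.45 | 0.4% |
| 0.25 (0.2) | 1 | (126 + 1026)/512 = 2.25 | √(0.45/0.45) = 1.00 | 5% |

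**4. Void reading, simulation.** Assumed: 57 participants, no true difference, within-participant SD 1 apart from rhythm, voids near 10, 13, 17, 21 and 7 h next morning (SD 1 h), acrophase 8 h, 4,000 runs per cell. Rejection (%) by the nominal 5% test:

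| Amplitude | Share 0 | 0.1 | 0.2 | 0.3 | 0.5 |
|---|---|---|---|---|---|
| 0 | 5.1 | 10.5 | 16.3 | 20.7 | 31.1 |
| 1 | 1.1 | 3.4 | 7.2 | 10.2 | 17.2 |
| 1.5 | 0.3 | 1.1 | 2.7 | 4.1 | 8.4 |

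With 5 to 8 voids per day the same grid runs from 0.6% to 37.2%. Both directions occur, and several cells are near nominal.

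**5. Candidate remedies**, same assumptions:

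- Day-within-participant intercept plus cosine and sine terms by setting: 3.9 to 5.8% over 33 scenarios, including 1 h shifts of void times or of acrophase in one setting.
- The same with time terms common to both settings: up to 13.6% when the acrophase shifts by 1 h.
- Time terms without the day intercept: 10.5 to 32.7% at shares 0.1 to 0.5.
- Paired test on the per-day MESOR: 4.2 to 5.9%.
- Paired test on raw day means, voids 1 h later in one setting, amplitude 1, acrophase 8 or 20 h: about 17, 11 and 9% at shares 0, 0.2 and 0.5.

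**6. Precision.** At shares 0, 0.2 and 0.5 the SD of the setting estimate is 0.098, 0.122 and 0.148 for the first remedy, and 0.105, 0.126 and 0.150 for the MESOR. The excess for the MESOR is therefore about 7, 3 and 1%. If the evening or next-morning void is missing, it rises to roughly 10 to 40%.

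**The case against.** The strongest reply is that the only explicit statement of a data unit, in section 2.9, is one pair of values per participant, and on that unit the model is sound. This stands as far as it goes. But section 2.9 describes the sample size calculation; nothing carries that unit into section 3.9.3 or says how 5 or more voids become one value.

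A second reply is that rhythm is already handled by the non-linear models and the per-day cosinor. That is correct: it would be wrong to infer that the SAP ignores the rhythm, and the per-participant, per-day cosinor fits are not affected. The gap lies in the linear model, and in the unstated nesting of the non-linear ones.

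A third reply is that the unstructured covariance matrix might describe correlation among repeated voids, which would weaken the case for a standard error that is too small. The sentence attaches it to the random intercepts, where it is a single variance, and an unstructured residual matrix is awkward with irregular void times and numbers. The phrase is unclear and does not close the gap.

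Two smaller matters carry no weight. Unequal numbers of voids are ordinary in mixed models. Section 3.7 says that "in Table 3 there is a description of the frequency and timing of relevant variable observations and assessments", while the table as shown lists only file, description, variable and type; that may be a cross-reference slip or a lost table.

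**Conclusion.** The point holds as a should-fix, with medium confidence. The record unit of the primary linear model is not stated. For the repeated voids that the plan collects, a participant intercept alone is not an adequate structure.

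A reader might infer that the primary test is anti-conservative. The SAP does not support that: the harm exists only if voids enter singly, and day variation and rhythm then pull in opposite directions. The figures of about 16% (day share 0.2, no rhythm) and under 1% (amplitude 1.5, no day effect) are illustrations under assumed variances, void times and acrophase. Nor is the sample size of 57 put in doubt; it follows from its own one-value assumption.

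**What to change.** State in section 3.9.3 what one record is.

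- **Preferred: single voids.** Add a random intercept for sampling day within participant, and cosine and sine terms of the recorded void time that may differ by setting, since section 3.9.1 itself tests whether amplitudes and acrophases differ. State the same nesting for the non-linear models.
- **Alternative: one value per setting.** Keep the participant intercept, name the creatinine-adjusted summary and set a minimum number of voids. A raw mean is sensitive to void timing. A per-day MESOR needs at least three distinct void times, and more to leave a residual variance; it would have to be fitted for every hormone, not only where a rhythm has been shown. It loses precision when a late void is missing, which is why the void-level model is preferred.

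In either case, say what the unstructured covariance matrix applies to, or delete the phrase. Hormones made binary under section 3.6 need their own stated model.

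The cost is SAP wording; void times and repeated voids are already planned. The preferred model adds one variance component, two time terms and their interactions with setting. Compared with the void-level model as written, confidence intervals may widen (about 2 times at day share 0.5 without rhythm) or narrow (to about 0.75 times at share 0 with amplitude 1.5).
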